LIFT is a multicentre phase III trial that randomises eligible babies to the experimental group receiving bLF added to breast milk or formula milk once daily, or to the control group receiving no bLF added to breast milk or formula milk. These strategies (hereafter referred to as treatments) are intended to continue until 34 weeks corrected gestation or for 2 weeks, whichever is longer, or until discharge home, if earlier.

The randomisation is performed using a centralised system that allocates patients in a 1:1 ratio via minimisation stratified by site, gender, birth weight ($<1000 \text{ vs} \ge 1000\text{-}1499\text{g}$), and according to whether the baby is from a single or multiple birth.

LIFT is masked (i.e. treatment allocation is concealed from investigators, clinicians, parents, study personnel) however a designated person (e.g. bedside nurse, pharmacist, member of milk kitchen staff, or any appropriate staff member) prepares the milk feed containing either bLF (treatment group) or nothing (control group).

- This analysis plan provides additional detail to the LIFT protocol (Version 2.0, 20JAN17, ACTRN12611000247976) on endpoint derivations and planned analyses. The health economic
- analyses described in the protocol are not detailed in this analysis plan.

2 Endpoints

analysis plan).

The primary endpoint for the study is morbidity-free survival to hospital discharge. The key secondary short-term endpoints comprise the 5 components of the primary composite endpoint.

The other secondary short-term endpoints are: time to reach full enteral feeds; number of blood transfusions; chronic lung disease; length of hospital stay; and, financial costs (out-of-scope for this

The following section provides detailed instruction on the derivation of endpoints. Any instances where the application of these instructions is unclear for a given baby will be resolved via blinded clinical review and documented.

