2.2 Survival to Hospital Discharge

- 17 Death is set to 'yes' if the following condition is met by data captured on the "Discharge
- 18 (DISCHARGE)" eCRF:
 - Was the baby alive at discharge? [itmSTATUS]='No'

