2.4 Necrotising Enterocolitis of Grade II or Higher at 36 Weeks Corrected Gestational

Age

The endpoint 'Proven episode of stage II NEC Higher at 36 Weeks Corrected Gestational Age' will be derived using items from the "36 Weeks (OUTCOMES)" eCRF. The table below indicates how the eCRF items (shown in columns A and B) will be used to determine NEC status (column C).

5 6

1

3

4

(A) Did the baby have a proven episode of necrotising enterocolitis [itmNEC]		(B) Please specify stage of disease [itmNECSTAGE]	(C) Proven episode of stage II or III NEC	
No		- 0	No	
Yes	AND	Stage I	No	
Yes	AND	Stage II or III	Yes	

7

8

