2.9 Chronic Lung Disease at 36 Weeks Corrected Gestational Age

The endpoint 'Chronic lung disease at 36 Weeks Corrected Gestational Age ' will be derived using items from the "36 Weeks (OUTCOMES)" eCRF. The table below indicates how the eCRF items (shown in columns A to C) will be used to derive chronic lung disease status (column D).

(A) Did the baby receive respiratory support at any time? [itmVENT]	(B) Is the baby still on supplemental oxygen at 36 weeks? [itmVENT36WKS]	(C) "Date last on supplemental oxygen or on assisted ventilation" [itmVENTDATE]		_ (D) Chronic lung disease	
No				No	
-	No			No	
7 -	Yes	AND	No more than 7 days before week 36 target	Yes	
	Yes	AND	More than 7 days before week 36 target	No	

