6.5 Analysis of Categorical Secondary Endpoints

- 26 Secondary categorical endpoints include: survival to hospital discharge (Section 2.2), brain injury
- 27 (Section 2.3), NEC (Section 2.4), LOS (Section 2.5), RoP (Section 2.6), chronic lung disease (Section
- 28 2.9), and survival and development status at 24-36 months corrected gestational age (Section 2.11).

29

- 30 Secondary categorical endpoints will be analysed using the same modelling approach applied to the
- 31 primary endpoint (i.e. a log-binomial model fitted using generalised estimating equations to
- 32 accommodate possible correlation of data between siblings from multiple births. If the log-binomial
- 33 model does not converge, a logistic model will be used).

- 35 Sensitivity analyses will be undertaken on the categorical morbidity endpoints (i.e. brain injury, NEC,
- 36 LOS, RoP, and chronic lung disease) in which any missing values due to death are treated as an
- 37 event. An analysis of survival to 36 weeks may also be undertaken as a sensitivity analysis. Estimates
- 38 of the treatment effect on survival to hospital discharge that are adjusted for adherence will be
- 39 produced using the methods detailed in Section 8.2 in a sensitivity analysis.

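### The sensitivity analysis for death recodes only missing values, but the lung-disease and brain-injury derivations can return 'No' for babies who died

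*SAP*

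**What the plan says.** Section 6.5 covers brain injury, NEC, late onset sepsis, retinopathy and chronic lung disease. For these it plans sensitivity analyses "in which any missing values due to death are treated as an" event. The rule acts on missing values only; a derived 'No' stays 'No'.

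Section 2.9 derives chronic lung disease from three items on the 36 Weeks eCRF: any respiratory support (A), "Is the baby still on supplemental oxygen at 36 weeks" (B), and the date last on oxygen or assisted ventilation (C). The result is 'No' if A is 'No', if B is 'No', or if B is 'Yes' and the date in C is more than 7 days before the week 36 target. No row covers death. Vital status sits on the Discharge eCRF (Section 2.2) and is not an input.

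Section 2.3 sets brain injury to missing only for scans performed outside their time limits: the first too late, or the second too early or too long after week 36, each with a further condition. Otherwise, if no listed injury is recorded, the value is 'No'. A scan that was never performed is not mentioned.

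Section 2 adds that instances "where the application of these instructions is unclear for a given baby will be resolved via blinded" clinical review.

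**The concern.** Section 6.5 assumes that death shows up as a missing morbidity value. Chronic lung disease is a status at 36 weeks, so it cannot be observed in a baby who died earlier. Yet 'No' is a literally true answer to whether a dead baby is still on oxygen. If that answer is entered, the main analysis counts the death as free of lung disease, and the sensitivity analysis meant to deal with deaths leaves it there. A baby with the same course and a blank item becomes an event. The result would then depend partly on how forms are completed, and a treatment that improves survival could appear to increase lung disease.

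The brain-injury route does not even need an answer to be entered. If no second scan exists, no missing rule fires and the default is 'No'. Brain injury is one of the five key secondary endpoints with adjusted p-values (Section 5).

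**Working it through.** The SAP states no figure on this point, so there is none to reproduce. The check has two parts.

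**1. Tracing the rules.** Take a baby who received respiratory support and died at 30 weeks, 6 × 7 = 42 days before the target. The last row is a baby who died early without ever having had support.

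| Form entries | Section 2.9 result | Section 6.5 sensitivity analysis |
|---|---|---|
| B 'No' | No | non-event |
| B 'Yes', last date 42 days before target | No | non-event |
| B blank | missing | event |
| A 'No' | No | non-event |

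For brain injury, suppose no grade 3 or 4 haemorrhage on the first scan and death before the second. No listed injury is recorded and no scan was performed at the wrong time, so the value is 'No' and Section 6.5 again leaves a non-event.

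**2. Illustrating the size for lung disease.** The SAP gives no death or lung-disease rates, so every input here is an assumption. Let s be the share of deaths before 36 weeks that are derived 'No'; the rest are missing and become events.

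*Illustration A.* Deaths are 7% control and 5% bLF. Lung disease is 35% in babies who would survive in either arm, and 70% in the 2% saved by bLF.

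- Lung disease in survivors, as a share of all babies: control 0.93 × 0.35 = 0.3255; bLF 0.3255 + 0.02 × 0.70 = 0.3395.
- s = 1 (also the main analysis if every death is derived 'No'): RR = 0.3395 / 0.3255 = 1.043.
- s = 0.5: (0.3395 + 0.025) / (0.3255 + 0.035) = 0.3645 / 0.3605 = 1.011.
- s = 0 (all deaths counted): (0.3395 + 0.05) / (0.3255 + 0.07) = 0.3895 / 0.3955 = 0.985.
- Babies alive at 36 weeks only: (0.3395 / 0.95) / (0.3255 / 0.93) = 0.357 / 0.350 = 1.021.

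*Illustration B.* Lung-disease risk c is the same in survivors of both arms, and d is the death rate. The event rate is c(1 − d) + d(1 − s). For c = 30% and deaths of 6% against 4%:

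- s = 0: (0.288 + 0.04) / (0.282 + 0.06) = 0.328 / 0.342 = 0.959.
- s = 1: 0.288 / 0.282 = 1.021.

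Over c = 20% to 40%:

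| Deaths, control vs bLF | RR, s = 0 | RR, s = 1 |
|---|---|---|
| 6% vs 4% | 0.935 to 0.972 | 1.021 |
| 10% vs 7% | 0.914 to 0.961 | 1.033 |
| 4% vs 6% | 1.028 to 1.069 | 0.979 |
| 6% vs 6% | 1.000 | 1.000 |

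With equal deaths only the rates move, for example from 34.2% to 28.2% at c = 30%.

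**The case against.** **Form behaviour is not shown.** A reader might infer that deaths are in fact counted as free of lung disease. The SAP does not support that. Skip logic and completion instructions are not part of it, and Section 6.5 itself speaks of values missing due to death, so its authors evidently expected blanks. If the eCRF forces a blank, the lung-disease rule works as intended. This stands and makes the lung-disease point conditional. It does not answer the brain-injury default, where a blank also gives 'No'.

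**Blinded review could catch these babies.** Possibly. But Section 2 sends only unclear cases to review, and an entry that matches a table row is not clearly one of them.

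**NEC and sepsis.** It is tempting to extend the error to these. The documents do not support it: the form asks "Did the baby have a proven episode of necrotising enterocolitis", and the sepsis item is likewise about episodes. 'No' is a valid observation up to death, so no derivation error is claimed there.

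**Size.** A reader might take 1.043 as harm produced by the form. On the same inputs, 1.021 remains in babies alive at 36 weeks, so about half comes from assuming that the saved babies are sicker. The shifts are also small against sampling error. With an assumed 500 to 1,000 babies per arm, a risk near 0.36 and siblings treated as independent, SE(log RR) = √(2 × 0.64 / (0.36n)), which is 0.08 to 0.06. The shift from 0.985 to 1.011 is 0.026 on the log scale, under half a standard error. The shift to 1.043 is 0.057, roughly 0.7 to 1 standard error.

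**Death is visible elsewhere.** True: survival is a key secondary endpoint, and survival to 36 weeks may be analysed. That helps a reader interpret the result but does not make the sensitivity analysis do what it says.

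**Conclusion.** The point holds as a mismatch between rules. Section 6.5 relies on missing values that Sections 2.9 and 2.3 do not reliably produce for babies who died. For lung disease the consequence depends on answers being entered for those babies; for brain injury it follows from the default taken literally. The number affected cannot be determined from the SAP.

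The effect on the relative risk is modest and arises only if survival differs between arms. On the assumed inputs the sensitivity estimate is 1.01 to 1.04 where counting all deaths gives 0.985, so it may cross 1. With equal mortality the relative risk is unchanged and only the event rates are understated.

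The primary composite is not affected: Section 2.1 already counts any death before discharge as an event, and lung disease is not a component.

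**What to change.** - **Section 6.5:** define the sensitivity endpoint as the morbidity or death before 36 weeks corrected gestation (for retinopathy, before discharge), using vital status and date of death whatever the item value.
- **Section 2.9:** add a first row setting chronic lung disease to missing (not assessable) for babies who died before the week 36 target.
- **Section 2.3:** set brain injury to missing when a required scan was not done because of death and no listed injury was seen.

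Section 6.6 already uses this construction for transfusions, where the supplementary endpoint is survival to 36 weeks without one. The cost is a few lines of text and one derived variable. No new data should be needed, since the possible analysis of survival to 36 weeks implies that the timing of death is available.

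There are two consequences to accept. The main lung-disease analysis becomes explicitly conditional on survival to 36 weeks and should be read beside the composite. For NEC and sepsis, the new wording makes the sensitivity endpoint a full death-or-morbidity composite. That is a choice in keeping with the aim of Section 6.5, not the correction of an error in those derivations.

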6.6 Analysis of Quantitative Secondary Endpoints

Number of blood transfusions (Section 2.8) will be treated as count data and analysed using a negative binomial regression model fitted using generalised estimating equations to accommodate possible correlation of data between siblings from multiple births.

Time to full enteral feeds (Section 2.7) and length of hospital stay (Section 2.10) will be analysed using a linear regression model fitted using generalised estimating equations to accommodate possible correlation of data between siblings from multiple births. An appropriate data transformation will be applied if continuous data are highly skewed. Based on a blinded review of interim data, a log transformation of time to full enteral feeds is anticipated to be appropriate, whereas the distribution of length of hospital stay is expected to be reasonably symmetric.

The following supplementary binary endpoints will be derived and analysed to accommodate instances where data on enteral feeding, transfusions, or length of hospital stay are missing/truncated due to death:

- Baby reached full enteral feed milestone within 7 days of randomisation (No versus Yes)
- Baby survived with no transfusions to 36 weeks GA (No versus Yes)
- Baby was discharged alive within 2 months of birth (No versus Yes)

These supplementary binary endpoints will be analysed as part of a sensitivity analysis using the modelling approach applied to the primary endpoint (i.e. a log-binomial model fitted using generalised estimating equations to accommodate possible correlation of data between siblings from multiple births. If the log-binomial model does not converge, a logistic model will be used).

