2.7 Time to Full Enteral Feeds

- 18 Time to full enteral feeds is measured from the date of randomisation to the date recorded in the
- eCRF corresponding to the 3^{rd} day on which enteral intake of ≥ 120 ml/kg/day was first achieved for
- 20 3 consecutive days.

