2.10 Length of Hospital Stay

- 7 Hospital length of stay is measured from the date of birth to the date the baby is discharged from
- 8 hospital.

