- 4 Descriptive statistics will be prepared to summarise the baseline characteristics of the study
- 5 participants by treatment allocation. Variables to be summarised include: gender, multiple birth,
- 6 birth weight, gestational age at birth, inborn/outborn, mode of delivery, and APGAR scores at 1 and
- 7 5 minutes.

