6.7 Safety Data Analysis

A descriptive analysis of SUSAR data will be conducted by treatment allocation. The event rate is expected to be low, and thus an exact test would be an appropriate choice to perform any formal comparisons between the two groups in the proportion experiencing a SUSAR.

7 Subgroup Analyses

Consistency of the treatment effect on the primary endpoint across subgroups will be tested by including a treatment-by-subgroup interaction term (along with the relevant main effect terms) as covariates in the analysis model (as specified in Section 6.4).

The subgroups of interest are: (i) birthweight <1000 g versus 1000-1499 g; (ii) randomised ≤72 hr versus >72 hr from birth; (iii) those who received versus did not receive probiotics by 36 weeks corrected gestation (note: this is a post-baseline covariate); (iv) ≤ 28 weeks versus >28 weeks gestation at birth. Because 'probiotic use by week 36' is a post-baseline covariate, an unbiased evaluation of its role as an effect-modifier will be attempted by categorising participating sites (NICUs) into tertile subgroups according to their propensity to use probiotics, and evaluating consistency of the treatment effect across these sub-groups.

Adjusted Analyses

8.1 **Stratification Factors**

Sensitivity of results obtained from the primary analysis of the primary endpoint to adjustment for stratification factors will be explored by included them as covariates in the model (See Section 6.4).

4 5 6

7

8

9

10

11

14

15

16

1

2

3

- Randomisation is stratified by gender, birth weight (<1000 g vs ≥1000-1499 g), according to whether the baby is from a single or multiple birth, and site (NICU). Given the modest number of patients at some sites, and the degree of variation in the number of babies recruited across sites (i.e. minimum is less than 10 babies and the maximum is more than 200 babies), sites will be categorised into larger groups that have a comparable pooled primary endpoint event rate. This will be done by estimating, in a blinded fashion, the event risk at each site pooled across treatments, and deriving 'risk classification' according to tertiles. Risk classification will be used as the covariate in the
- 12

13 adjusted analyses in preference to 'individual site'.

8.2 **Treatment Compliance**

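### Length of hospital stay is counted from birth but modelled without gestational age at birth, so its confidence interval is wider than the collected data require

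*SAP*

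**What the plan says.** SAP Section 6.6 sets the model: "Time to full enteral feeds (Section 2.7) and length of hospital stay (Section 2.10) will be analysed using a linear regression model". It adds GEE for sibling correlation and a rule for transforming skewed data (a log for time to full feeds, probably none for stay). It mentions no covariate.

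The two endpoints have different starting points:

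- Section 2.10: "Hospital length of stay is measured from the date of birth to the date the baby is discharged from" hospital.
- Section 2.7: "Time to full enteral feeds is measured from the date of randomisation to the date recorded in the" eCRF for the feeding milestone.

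Gestational age at birth appears in two places. Section 6.2 lists it among the baseline variables to be summarised ("gestational age at birth, inborn/outborn, mode of delivery"). Section 7 uses it, split at "≤ 28 weeks versus >28 weeks", as a subgroup factor for the primary endpoint. Section 1 (Introduction) gives the minimisation factors as site, gender, birth weight split at 1000 g and single or multiple birth. Gestational age is not among them.

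Covariate adjustment is confined to Sections 6.4 and 8.1. The latter reads "Sensitivity of results obtained from the primary analysis of the primary endpoint to adjustment for" the stratification factors. It therefore covers one endpoint, as a sensitivity analysis, and does not include gestational age.

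**The concern.** A stay counted from birth contains gestational age by construction. Two babies who go home at the same corrected age, but were born six weeks apart in gestation, differ by six weeks of stay whatever their treatment. A model with treatment alone treats that known, pre-randomisation difference as noise.

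Minimising on birth weight at 1000 g balances gestation in part. An unadjusted model still leaves the corresponding variance in the reported standard error. What is at stake is the width of the interval for the stay difference: it is wider than it needs to be, and a modest real difference is harder to see.

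**Working it through.** The SAP states no SD, correlation, target difference or power for length of stay, so there is no figure to reproduce. All SDs below are assumptions.

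**Step 1, identity.** Stay = corrected age at discharge − gestational age at birth. If the two terms on the right are independent, the share of the variance of stay due to gestation is

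R² = Var(GA) / [Var(GA) + Var(discharge age)].

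**Step 2, simple formula.** In a linear model with independent babies, adjusted SE / unadjusted SE = √(1 − R²).

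**Step 3, the planned type of model.** Siblings share gestation, and a GEE with within-family correlation already draws on contrasts between siblings, in which gestation cancels. The simple formula therefore overstates the gain. A simulation of an exchangeable linear GEE, with and without gestational age, gives the more relevant ratio. Its settings were:

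- 400 families, 18% of them twin pairs, and 150 replicates
- each baby allocated separately 1:1 with no treatment effect
- 30% of the discharge-age variance shared within families
- gestational age SD 2.5 weeks (variance 6.25)

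| SD of corrected age at discharge | R² | √(1 − R²) | Simulated SE, unadjusted → adjusted (days) | Ratio | Reduction |
|---|---|---|---|---|---|
| 2 weeks | 6.25/10.25 = 0.61 | 0.62 | 1.84 → 1.27 | 0.69 | 31% |
| 3 weeks | 6.25/15.25 = 0.41 | 0.77 | 2.36 → 1.89 | 0.80 | 20% |
| 4 weeks | 6.25/22.25 = 0.28 | 0.85 | 2.89 → 2.53 | 0.87 | 13% |

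The SEs in days belong to the simulated sample size, not to the trial; only the ratios carry over. The mean estimated effect was within 0.09 days of the true value of zero in both analyses, so neither shows bias.

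**Step 4, sensitivity to the assumed SDs.** With a gestational age SD of 2 to 3 weeks and a discharge-age SD of 2 to 5 weeks, R² runs from 4/29 = 0.14 to 9/13 = 0.69. By the simple formula the SE ratio then runs from 0.93 to 0.55. As Step 3 shows, the actual gain would be somewhat smaller.

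**Step 5, time to full enteral feeds.** The clock starts at randomisation, so the identity in Step 1 does not apply. Any gain depends on how well gestation predicts feeding progress, for which the SAP gives nothing. An assumed R² of 0.05 to 0.30 gives √0.95 = 0.975 to √0.70 = 0.837, an SE 2.5% to 16% smaller.

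**The case against.** The strongest reply is that nothing here is an error. Under randomisation the unadjusted linear comparison is unbiased and its test is valid. The SAP leaves its main models unadjusted throughout, including that for the primary endpoint. Stay is listed among the other secondary endpoints, below the five key ones, with no multiplicity control and no stated power. Every size above rests on assumed SDs. Section 6.6 itself recognises that stay can be truncated by death. If the least mature babies die early, their short stays would weaken the link with gestation and reduce the gain. Birth weight is correlated with gestation, so a model that also held birth weight would gain less from adding gestational age.

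All of this stands, and it limits the point to efficiency on a lower-tier endpoint. It does not make the matter one of taste. In a linear model, a baseline covariate leaves the mean difference being estimated unchanged. The covariate is already in the plan, and for stay the link is arithmetic rather than conjectural. Section 6.6 is silent on covariates rather than forbidding them, but the explicit limits in Sections 6.4 and 8.1 make an unadjusted model the natural reading.

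A reader might infer three stronger claims that the SAP does not support:

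- **That chance imbalance in gestation would invalidate the comparison.** Such imbalance is already reflected in the unadjusted standard error and the 5% error rate.
- **That a given amount of power is lost.** The SAP states no power for this endpoint from which a loss could be counted.
- **That the same argument covers time to full feeds.** It does not, because that endpoint starts at randomisation.

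**Conclusion.** The point holds for length of stay as an avoidable loss of precision, not as a fault in validity. Under the central assumptions (gestational age SD 2.5 weeks, discharge-age SD 2 to 4 weeks, discharge age independent of gestation, siblings allocated separately), adjustment would shorten the standard error by about 31% to 13%. Deaths before discharge would lower these figures. For log time to full feeds the case is weaker, and the gain may be negligible.

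Section 6.2 lists gestational age as a variable to summarise and does not say that it is complete for every baby. The 36-week endpoints cannot be dated without it, however, so large gaps are unlikely.

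**What to change.** In Section 6.6, add that the GEE linear model for length of hospital stay will include gestational age at birth as a continuous covariate. Check linearity on blinded data, as was done for the choice of transformation, and report the unadjusted estimate alongside. Birth weight group, gender, single or multiple birth and the site risk class of Section 8.1 can go into the same model. The extra gain from gestational age beyond birth weight would then be smaller than the figures above.

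The same covariate may be used for log time to full enteral feeds, without an expectation of a material gain.

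The cost is a sentence or two of SAP text and one listed baseline variable, with no new data or patients and no change of estimand. It should be written in before unblinding, because a covariate added later would look data-driven.
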